APPENDIX I. PUBLICATION POLICY

All unpublished information given to the investigator by the sponsor shall not be published or disclosed to a third party without the prior written consent of the sponsor.

The results of this study may be published or presented at scientific meetings. If this is foreseen, the investigator agrees to submit all manuscripts or abstracts to the sponsor before submission. This allows the sponsor to protect proprietary information and to provide comments.

The sponsor will comply with the requirements for publication of study results:

"Recommendations for the Conduct, Reporting, Editing, and Publication of Scholarly Work in Medical Journals" (ICMJE). Publication of the results will occur in a timely manner according to applicable regulations. In accordance with standard editorial and ethical practice, the sponsor will generally support publication of multicenter studies only in their entirety and not as individual investigational center data. In this case, a coordinating investigator will be designated by mutual agreement.

Authorship will be determined by mutual agreement and in line with International Committee of Medical Journal Editors authorship requirements:

- substantial contributions to the conception or design of the work; or the acquisition, analysis, or interpretation of data for the work
- drafting the work or revising it critically for important intellectual content
- final approval of the version to be published
- agreement to be accountable for all aspects of the work in ensuring that questions related to the accuracy or integrity of any part of the work are appropriately investigated and resolved

The publications committee established by the sponsor will oversee this process. Additional publications may follow. Policies regarding the publication of the study results are defined in the financial agreement.

No patent applications based on the results of the study may be made by the investigator nor may assistance be given to any third party to make such an application without the written authorization of the sponsor.

20.1. Intent-To-Treat Analysis Set41

20.2. Modified Intent-To-Treat Analysis Set42

20.3. Safety Analysis Set43

20.4. Predicting Severe CAE/Moderate CAE from Multiple Device-Use-Measures44

21. REFERENCES45

LIST OF TABLES

Table 1: Study Procedures and Assessments13
Table 2: Systemic Glucocorticoid Treatment Equivalent to 10 mg of Prednisone.....31

AMENDMENT HISTORY

The Statistical Analysis Plan for study ABS-AS-30064 (study protocol with amendment 02 dated 22 February 2017) has been amended and reissued as follows:

Amendment number	Date	Author(s)	Summary of Changes	Reason for Amendment
01	9 April 2018	[REDACTED]	Sections 3, 5.2, 5.10, 7, and 10 updated to indicate that all endpoint and safety analyses will use the ITT analysis set.	Decision by study team
			Section 4.4 updated to indicate whichever comes first.	Clarification
			Section 4.6 updated to remove the bullets regarding the derivation of Study Day X TDS, Study Day X nighttime average sleep latency time, Study Day X longest nighttime wake episode, and Study Day X total time awake at night.	Clarification as this will not be done
			Sections 7.3.1 and 7.4.1 updated to remove the statements regarding the missing data handling for Study X TDS, Study Day X nighttime average sleep latency time, Study Day X longest nighttime wake episode, and Study Day X total time awake at night.	Clarification as this will not be done
			Section 7.5.2 updated with modified analyses.	For this exploratory study, analyses methods were updated in the spirit of the protocol to better address study objectives and to align with the ancillary analytics report.
			Section 7.5.2.4 updated.	Clarification
			Section 7.5.3 updated to clarify that the analyses will be done by the data analytics group.	Clarification
			Section 10.4 updated to clarify the definition of treatment emergent.	Clarification

LIST OF ABBREVIATIONS AND DEFINITIONS OF TERMS

Abbreviation	Term
ABS	albuterol sulfate
ACQ-5	Asthma Control Questionnaire-5
BMI	body mass index
CAE	clinical asthma exacerbation
CI	confidence interval
CRF	case report form (refers to any media used to collect study data [ie, paper or electronic])
CSR	clinical study report
CTCAE	Common Terminology Criteria for Adverse Events
DPI	dry powder inhaler
eMDPI	multidose dry powder inhaler with an eModule
ICH	International Council for Harmonisation
IMP	investigational medicinal product
ITT	intent-to-treat
KM	Kaplan Meier
MDI	metered dose inhaler
MedDRA	Medical Dictionary for Regulatory Activities
MIF	maximal inhalational flow
mITT	modified intent-to-treat
PT	preferred term
R&D	Research and Development
SABA	short-acting beta agonist
SAMA	short-acting muscarinic antagonist
SD	standard deviation
SDI	sleep disruption index
SOC	system organ class
SOP	standard operating procedure
TDS	total daily steps
ULN	upper limit of normal
WHO Drug	World Health Organization Drug Dictionary

INTRODUCTION

This Statistical Analysis Plan describes the planned analysis and reporting for Teva Branded Pharmaceutical Products R&D, Inc. Study ABS-AS-30064 (A 12-Week, Open-Label Study to Evaluate the Relationship Between Use of Albuterol Multidose Dry Powder Inhaler with an eModule (eMDPI), an Inhaled Short-Acting Beta Agonist (SABA) “Rescue” Agent with an eModule, and Exacerbations in Patients (18 Years of Age or Older) with Asthma), and was written in accordance with standard operating procedure (SOP) GBP_RD_702 (Statistical Analysis Plan).

The reader of this Statistical Analysis Plan is encouraged to read the study protocol for details on the conduct of this study, the operational aspects of clinical assessments, and the timing for completing the participation of a patient in this study. The Statistical Analysis Plan is intended to be in agreement with the protocol. However, the Statistical Analysis Plan may contain more details regarding these particular points of interest, or other types of analyses (eg, other endpoints). When differences exist in descriptions or explanations provided in the study protocol and this document, the Statistical Analysis Plan prevails; the differences will be explained in the clinical study report (CSR) or in this document.

1. STUDY OBJECTIVES AND ENDPOINTS

1.1. Objectives and Endpoints

The objectives of this study are to explore the pattern and amount of albuterol use (as captured in the ABS eMDPI), alone or in combination with other study data, preceding a clinical asthma exacerbation (CAE) and in particular, a severe CAE (as diagnosed by the investigators per the protocol). The hypothesis is that albuterol use will increase several days prior to a severe CAE and can serve as a marker of asthma deterioration.

The endpoints of the trial are the primary outcome measure (ie, CAE/severe CAE) and the primary outcome predictor (ie, albuterol use) alone or in combination with secondary predictors (ie, other study data). Multiple correlates of CAE/severe CAE focused on albuterol use, alone or in combination with other study data, will be modeled to determine which patterns best predict the subsequent development of CAE/severe CAE.

For albuterol use, parameters of interest will include (1) the total number of inhalations in the days preceding the peak of a severe CAE, (2) the number of days prior to the peak of a severe CAE when albuterol use increased, and (3) the number of albuterol uses in the day preceding a severe CAE. Therefore, endpoints are not designated as either primary or secondary.

In addition to albuterol use, inspiratory flow values (maximal inhalational flow [MIF], inhalational volume, inhalation duration, and time to MIF), sleep disruption index (SDI), total daily steps (TDS), and baseline information regarding disease state and demographics will be studied. These data will be analyzed using both a univariate and multivariate approach to determine which patterns best predict the subsequent development of a moderate CAE or severe CAE. Inspiratory flow values are obtained from the eMDPI, SDI is obtained for a subset of patients who agree to participate at specific sites (n=100) from an accelerometer worn on the wrist, and TDS is obtained for a subset of patients who agree to participate at specific sites (n=100) from an accelerometer worn on the ankle. Baseline disease state and demographic information will be obtained at screening.

An additional objective for this study is to evaluate the safety of ABS eMDPI use in patients with exacerbation-prone asthma.

The safety endpoints for this study include:

- adverse event data and
- physical examinations

2. STUDY DESIGN

2.1. General Design

This is a 12-week, multicenter, open-label study to evaluate the relationship between as-needed usage of ABS eMDPI and CAE/severe CAE in adult patients at least 18 years of age with exacerbation-prone asthma. ABS eMDPI is a rescue/reliever agent that includes an eModule on top of the approved PROAIR[®] RESPICLICK inhaler. The on-board electronics and power source are fully integrated into the inhaler and are designed to operate for the life of the inhaler without intervention. The electronic module records timestamped, pre-defined events such as cap open and inhalation parameters. The inclusion of the eModule has been shown to have no impact on the dose delivery compared with the approved product without the eModule.

The study will consist of a 2-week screening period and a 12-week intervention period.

After providing written informed consent, patients will complete a screening visit (visit 1) to determine eligibility for the study. Patients will provide medical history (including prior medications), complete a physical examination, pregnancy test, and review asthma exacerbation history. Eligible patients will return to the investigational center within 2 weeks for the baseline visit (visit 2). Those meeting entry criteria will be trained on the use of the eMDPI device and, upon demonstrated competency, will receive ABS eMDPI devices for use as rescue bronchodilators during the study. The screening visit and baseline visit may be combined.

Patients must use ABS eMDPI as their ONLY rescue agent for the duration of their participation in this study and will be advised to place any current rescue pills, inhalers, or nebulizers, including SABA, short-acting muscarinic antagonists (SAMA), or SABA/SAMA combination into storage. Patients may continue use of other asthma and non-asthma medications as advised by their physician without changes unless deemed necessary by their physician. Patients will be managed according to routine clinical practice by their treating physician with no specific study related instructions provided other than those on the proper use of ABS eMDPI.

Patients will be contacted by phone on a monthly basis for the collection of information about asthma exacerbations and treatments, concomitant medications, and adverse events. A review of the instructions for the use of ABS eMDPI and the procedure for replacement and return of ABS eMDPI will also occur during the monthly call.

Patients will receive initial eMDPI devices at visit 2 and subsequently by courier on Day 21. Patients will be instructed to return all inhalers to the site at the last study visit or early termination. At the last study visit or early termination, patients will be queried for adverse events, concomitant medications, and asthma exacerbations; a physical examination will be completed; and the patient will subsequently be discharged from the trial.

Two subsets of patients who agree to participate at specific sites and wear an accelerometer either on the wrist to measure SDI (n=100) or on the ankle to measure TDS (n=100) will be instructed on the proper use of these devices at the baseline visit (visit 2). The devices will be worn throughout the 12 week intervention period and will be returned to the investigational center at the final visit or upon early termination (visit 5).

The end of study is defined as the last visit of the last patient.

Study procedures and assessments with their timing are summarized in [Table 1](#).

Table 1: Study Procedures and Assessments

Study period	Pre-intervention	Intervention				
Visit number	V1	V2	V3 ^a	V4 ^a	Vz	V5
Day and allowed time windows	Day -14 to Day 1	Day 1	Day 28 ±7 days	Day 56 ±7 days	Up to 14 days After CAE Start Date	Day 84 ±14 days
Procedures and assessments	Screening	Baseline	Phone visit	Phone visit	Exacerbation visit	Final /early termination visit
Informed consent	X					
Inclusion and exclusion criteria	X	X				
Assign patient number	X					
Medical history	X					
Prior medication and treatment history	X					
Physical examination, including height and weight ^b	X				X	
Vital signs measurement ^c	X					
Urine pregnancy test for women of childbearing potential	X					X
Complete ACQ-5	X					
Inform patients of study compliance for eMDPI and accelerometer, and requirement for provider visit in the event of CAE	X	X	X	X		
Assess for asthma exacerbations	X	X	X	X		X
Adverse events inquiry		X	X	X	X	X
Wearable accelerometers: dispense, training, and collection ^d		X				X
ABS eMDPI: dispense, training, collection, and accountability ^e		X	X			X
Concomitant medication inquiry	X	X	X	X	X	X

^a Investigational centers must obtain source documentation of all asthma exacerbations that occur during the treatment period to confirm the accuracy of the information obtained from the patient.

^b Height will be measured at the screening visit only.

^c Vital signs measurements will include blood pressure, respiratory rate, and heart rate (pulse rate).

^d Wearable accelerometers for a subset of patients who consent to participate at specific sites will be dispensed at visit 2 and SDI and TDS data will be collected continuously from visit 2 through visit 5 via the wearable accelerometer. Instructions for proper use of the devices will be provided to patients at visit 2. The devices will be collected at visit 5.

^e Patients will receive initial ABS eMDPI devices at visit 2 and subsequently by courier on Day 21. Patients will be instructed to return all inhalers to the site at the last study visit or early termination. Instructions for dispensing, proper clinical use, and collecting ABS eMDPI will be provided to patients at visit 2 and reviewed during the monthly calls.

ABS=albuterol sulfate; CAE=clinical asthma exacerbation; SDI=sleep disruption index; TDS=total daily steps; eMDPI=multidose dry powder inhaler with an eModule; IMP=investigational medicinal product; V=visit. Screening and baseline visits may be combined.

2.2. Randomization and Blinding

This is an open-label study and there will be no blinding and no randomization.

2.3. Sample Size and Power Considerations

Assuming an expected dropout rate of 10%, it is recommended that 400 patients be enrolled so that 360 evaluable patients complete the study. The rationale is based on a review of the relevant literature, as follows.

Based on previous studies of a poorly-controlled exacerbating asthma cohort ([Bateman et al 2015](#), [Ko et al 2012](#), [McCarren et al 1998](#), [Quezada et al 2016](#)), it is expected that between 20% and 25% of subjects at risk in this patient population will experience a CAE (event) over 3 months, resulting in 72 to 90 expected CAE events in this study. In addition, it is expected that approximately 6.7% and 15% ([Bousquet et al 2007](#), [Ko et al 2012](#), [Kuna et al 2007](#), and [Rabe et al 2006](#)) of subjects at risk in this patient population will experience moderate and severe events, respectively, resulting in approximately 78 events (24 moderate events and 54 severe events) in this study.

This sample size (n=400 patients; 72 to 90 CAE events) is considered adequate for fulfillment of the study objectives using univariate and multivariate analyses to evaluate the relationship of the pattern of albuterol use, inspiratory flow, SDI, and TDS data associated with the subsequent development of a moderate CAE or severe CAE. Per the study by Patel ([Patel et al 2013](#)), a statistically significant relationship was established between prior mean daily SABA usage at baseline and subsequent CAE, studying 45 exacerbations ($p < 0.006$).

In the present study, approximately 72 to 90 CAE events are desired for this trial because the model's fitting of the current study involves the analysis of multiple predictors as described in more detail below.

Risk models published in the literature have typically included between 4 and 6 covariates/risk factors ([Bateman et al 2015](#), [Greenberg et al 2012](#), [Quezada et al 2016](#)) to examine the relationship between possible risk factors and a disease. When there is more than 1 covariate (risk factor) in the model, multiple logistic regression may be used to estimate the relationship of a specific covariate of interest (ie, albuterol use) to a primary outcome (ie, CAE), adjusting for the other/remaining covariates (risk factors). In this case, the required sample size to estimate such a relationship is greater than that for univariate logistic regression. The number of events per variable has been suggested as a criterion for the size of a data set ([Peduzzi et al 1996](#), [Harrell et al 1984](#), [Laupacis et al 1997](#)). The rule of thumb when building logistic regression models is 1 predictor variable for every 10 events ([Peduzzi et al 1996](#), [Vittinghoff and McCulloch 2007](#)). Therefore, this sample size would be adequate for predicting the primary outcome (CAE) using multiple logistic regression, including the covariate of primary interest (ie, albuterol use) and the remaining multiple predictors (inspiratory flow values, SDI, and TDS) as potential risk factors for CAE in the model for this patient population.

2.4. Sequence of Planned Analyses

2.4.1. Planned Interim Analyses

There will be no formal interim analysis for this study.

2.4.2. Final Analyses and Reporting

All analyses identified in this Statistical Analysis Plan will be performed after the end of the study as defined in the study protocol.

This Statistical Analysis Plan and any corresponding amendments will be approved before database lock, in accordance with SOP GBP_RD_702 (Statistical Analysis Plan).

3. ANALYSIS SETS

3.1. Intent to Treat Analysis Set

The intent-to-treat (ITT) analysis set will include all enrolled patients regardless of whether a patient took any investigational medicinal product (IMP). A patient is considered enrolled according to the status reported in the database. This analysis set will be used for endpoint analysis and safety analysis.

3.2. Modified Intent-to-Treat Analysis Set

The modified intent-to-treat (mITT) analysis set is a subset of the ITT analysis set that will include patients who used the IMP at any time during the study and patients who did not use the IMP at any time during the study provided these patients complied with study requirements and the data from the ABS eMDPI inhalers were successfully downloaded at the end of the study.

3.3. Safety Analysis Set

The safety analysis set will include all enrolled patients who receive at least 1 dose of the IMP.

3.4. Wrist Accelerometry Analysis Set

The wrist accelerometry analysis set is a subset of the mITT analysis set that will include patients who wore a wrist accelerometer with sufficient memory to capture 12 weeks of data during study participation and for whom data from the wrist accelerometer were successfully downloaded at the end of the study.

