6.1.4. Accelerometry

From a subset of patients who agree to participate at specific sites, SDI and TDS data will be downloaded using extraction software directly from the wearable accelerometer devices collected from the patients at their final study visit or transmitted to the central data center via Wi-Fi on a daily basis. A description of the analysis is provided in the Statistical Analysis Plan.

The wearable Philips accelerometer falls into a product classification that the Food and Drug Administration (FDA) has deemed 510(k) exempt.

See the User Guide for a description of care and use of wearable devices.

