3.5. Ankle Accelerometry Analysis Set

The ankle accelerometry analysis set is a subset of the mITT analysis set that will include patients who wore an ankle accelerometer with sufficient memory to capture 12 weeks of data during study participation and for whom data from the ankle accelerometer were successfully downloaded at the end of the study.

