4.6. Handling Withdrawals and Missing Data

Any data that was collected prior a patient's withdrawal from the study will be used for analysis and presented in the data listings.

The following imputation rules will be used;

- If the return date of the last ABS eMDPI device returned is missing the patient's last date of contact or study completion date will be used as the return date (see Section 4.4 and Section 10.2).
- Adverse events or serious adverse events with missing start dates will be considered treatment emergent (see Section 10.4).
- If a patient never used the ABS eMDPI during the study or download of a given ABS eMDPI device was not successful, study day and weekly inhalational flow values will be missing. If download of a given wrist or ankle accelerometer was not successful, TDS and SDI indices will be missing. These missing data will not be imputed.
- In the derivation of Study Day X Inhalation flow values, if there was no albuterol use on Study Day X , then the closest preceding nonmissing Study Day Inhalation' is used as the 'Study Day X Inhalation' and the inhalational flow values for Study Day X are assigned accordingly (see Section 7.2.1).
- For patients in the ankle accelerometry analysis set if no step data are available for study day 1 through study day 14, the 'baseline TDS' is the first available TDS after study day 14 (see Section 4.2.4).
- For patients in the wrist accelerometry analysis set if no sleep parameter data are available for study day 1 through study day 14, the 'baseline value of a given sleep parameter' is the first available valid sleep parameter value after study day 14 (see Section 4.2.5).

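### SAP 3.4 and 3.5 remove an accelerometer wearer from every step or sleep summary if the device lacked 12-week memory, although a shorter record can be fully usable

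*SAP*

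**What the plan says.** SAP 3.4 and 3.5 set three conditions for each accelerometry set.

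- **Parent set.** "The wrist accelerometry analysis set is a subset of the mITT analysis set", and the ankle set is nested in the same way.
- **Device capacity.** The ankle set takes "patients who wore an ankle accelerometer with sufficient memory to capture 12 weeks of data during study participation"; the wrist set takes patients who wore a device "with sufficient memory to capture 12 weeks of data during study participation and for whom data from the wrist accelerometer were successfully downloaded".
- **Download.** The accelerometer data must have been downloaded successfully at the end of the study.

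SAP 7.3.1 computes total daily steps (TDS) only for the ankle set, and SAP 7.4.1 computes the sleep disruption index (SDI) only for the wrist set. SAP 4.6 adds that TDS and SDI are missing, and not imputed, when an accelerometer download fails.

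Protocol 6.1.4 gives two routes for the data: extraction from the returned device, "or transmitted to the central data center via Wi-Fi on a daily basis". Protocol 9.3 bases the analyses on observed data and sets no device-capacity test.

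**The concern.** The memory condition tests what a device could hold, not whether the data it holds are valid. SAP 7.3.2.1 and 7.4.2.1 summarise steps and sleep at 1, 3, 5, 7, 10, 14 and 21 days before the CAE peak. SAP 4.2.4 and 4.2.5 take baseline from days 1 to 14. None of this needs 12 weeks of capacity, and neither document gives a reason for requiring it.

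The result is uneven. A patient who withdraws after two weeks on a large-memory device stays in. A patient with six complete weeks on a smaller device is removed entirely.

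The download condition has a narrower fault. On its literal wording, days already sent by Wi-Fi do not count if the end-of-study download fails.

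Precision is at stake, with possible selection, in the smallest part of the trial. The step and sleep summaries are also split into moderate and severe CAEs, so single patients count.

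**Working it through.** **The plan's own figures (SAP 2.3).** 400 × 0.90 = 360 evaluable. 360 × 0.20 = 72 and 360 × 0.25 = 90 CAEs. 360 × 0.067 = 24.1 moderate and 360 × 0.15 = 54 severe, together 78.1. All reproduce. No figure is given for the accelerometry sets beyond 100 patients each.

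**Expected CAE patients per subset**, assuming the study-wide rates apply:

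- With 10% dropout: 100 × 0.90 = 90; 90 × 0.20 = 18 and 90 × 0.25 = 22.5.
- With no dropout: 100 × 0.20 = 20 and 100 × 0.25 = 25.
- By severity, with 10% dropout: 90 × 0.15 = 13.5 severe and 90 × 0.067 = 6.0 moderate.

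**Loss by share excluded.** The share f is an assumption, because the documents give neither device memory nor a count of devices that fall short. Loss = f × expected CAE patients.

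| f | 10% dropout (18 to 22.5) | No dropout (20 to 25) |
|---|---|---|
| 10% | 1.8 to 2.25 | 2.0 to 2.5 |
| 20% | 3.6 to 4.5 | 4.0 to 5.0 |
| 30% | 5.4 to 6.75 | 6.0 to 7.5 |
| 50% | 9.0 to 11.25 | 10.0 to 12.5 |

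**How much could be recovered.** Assume that CAEs are spread evenly over 84 days, that a full device stops recording, and that every exclusion is due to memory. A 4-, 6- or 8-week device then covers 28/84 = 33%, 42/84 = 50% or 56/84 = 67% of CAE dates. At f = 10% with six weeks of memory, 0.5 × (1.8 to 2.5) = 0.9 to 1.25 CAE patients per subset would return.

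**A usable short record.** Take a six-week device recording days 1 to 42 and a CAE peaking on day 36. Days 1 to 14 give the baseline. The 21-day look-back runs from day 36 − 21 = 15 to day 35. Both lie wholly inside the record, yet the patient is excluded.

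**Who the mITT condition removes.** SAP 3.2 says the set "will include patients who used the IMP at any time during the study", so every inhaler user qualifies. Only never-users face the further conditions that they complied and that "the data from the ABS eMDPI inhalers were successfully downloaded at the end of the study".

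**The case against.** The strongest reply is that the loss may be zero. The documents do not say that any short-memory device was used, or that Wi-Fi transfer took place for a patient whose final download failed. They also do not say whether a full device stops or overwrites. If it overwrites, the last weeks survive and the day 1 to 14 baseline is lost. All of this stands: it limits the size claimed and means the remedy needs a baseline safeguard. It does not justify a capacity test that can only remove recorded data.

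A second reply is that truncated records bring unequal observation time, which affects the maximum change from baseline compared by CAE status. That is true but small, and the plan already accepts it for early withdrawals.

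A reader might infer that partial data in general are thrown away. The documents do not support that. Inside the sets, weekly steps, sleep latency and time awake are averaged over nonmissing days, and baseline may fall after day 14.

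A reader might also infer that SAP 4.6 contradicts these definitions, because it says "Any data that was collected prior a patient's withdrawal from the study will be used for analysis". It does not: that sentence concerns withdrawn patients, who stay in if their device qualifies and is downloaded. The failed-download sentence in 4.6 agrees with 3.4 and 3.5.

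Nor is the mITT condition a large leak. Patients have uncontrolled asthma and the study inhaler is their only permitted rescue agent, so few patients with a CAE are likely to be never-users. Some step and sleep summaries also need inhaler data, because they are anchored to the first day above 4, 12 or 20 inhalations.

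**Conclusion.** The point holds for the memory condition and, on the literal wording, for transmitted data when the final download fails. A failed download with no transmitted copy leaves nothing to recover.

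The actual loss cannot be computed. As an illustration, each 10% of a subset excluded costs about 2 (1.8 to 2.5) of 18 to 25 expected CAE patients. This assumes study-wide CAE rates and exclusions unrelated to CAE risk. With six weeks of memory and even timing, about half would be recoverable. It would be tempting to state a firm number of CAEs lost, but that would need device failure rates that neither document gives.

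The summaries in SAP 7.3 and 7.4 are descriptive, so no error rate or power statement is affected. The predictive models are left to the data analytics group (SAP 7.5.3), with no statement that these sets govern them.

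The populations also need reconciling. SAP 7 assigns all endpoint analyses to ITT, 3.4 and 3.5 stay inside mITT, and 7.3.2.1 and 7.4.2.1 refer to accelerometry *cohorts* that are not defined. SAP 20 does not list the accelerometry sets among the changes from the protocol.

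Overall, this is a cheap improvement that keeps observed data, not a flaw that undermines the trial.

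**What to change.** 1. In SAP 3.4 and 3.5, delete the 12-week memory condition. Define each set as enrolled wearers with valid accelerometer data from the final download or from transmission, and state what counts as a valid day.
2. Treat days outside the recorded period as missing.
3. Restrict change-from-baseline summaries to patients with recorded data in days 1 to 14, or flag the others. Without this, a patient with a single recorded day would have a baseline equal to that day and a change of zero.
4. Show the number of patients per week, and the number excluded with reasons.
5. Align the failed-download sentence in SAP 4.6, and use *cohort*, *analysis set* and ITT consistently in SAP 7, 7.3 and 7.4.

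The cost is SAP wording and small additions to the tables; no new data are collected. The downside is that recording length will vary between patients, which affects the maximum-change summaries. Report recorded days by CAE status so that this can be seen.
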